#### **5.5.2.3 Demographics**

For determining age when the date of birth is not known completely, a missing day only will be imputed as the 15th, a missing day and month will be imputed as the 2nd of July which is day 183 in the year.

#### **5.5.2.4 Concomitant Medications**

Missing concomitant medication dates will be handled in a similar fashion as described for AEs in Section 5.5.2.2.

### **5.6 Interim Analyses**

No Interim Analyses are planned for this study.

## **6. Statistical Analyses**

### **6.1 Patient Disposition**

Patient Disposition recorded at Screening will be summarized by absolute counts (n) and percentages (%). Percentages will be based on the number of patients with data. This will be presented for the Screening Analysis Set and for the ITT Analysis Set.

### **6.2 Protocol Violations**

Protocol Violations will be summarized by absolute counts (n) and percentages (%). Percentages will be based on the number of patients with data.

### **6.3 Demographics and Baseline Patient Characteristics**

Demographics include collected and derived, continuous and categorical variables. Continuous variables will be summarized by the number of patients, mean, SD, median, minimum and maximum values. Categorical variables will be summarized by absolute counts (n) and percentages (%). Percentages will be based on the number of patients with data. This will be presented for the Screening Analysis Set, Safety Analysis Set, ITT Analysis Set and PP Analysis Set.

### **6.4 Medical History**

Medical History will be summarized by absolute counts (n) and percentages (%). Percentages will be calculated based on the number of patients. This will be presented for the Safety Analysis Set

Separate summaries will also be presented for Relevant HAE history and Relevant HAE Attack History.

### **6.5 Concomitant Medication**

Concomitant Medications will be summarized by absolute counts (n) and percentages (%) for each PT within ATC class. Percentages will be calculated based on the number of patients at risk. This will be presented for the Safety Analysis Set

### **6.6 Treatment Compliance**

Not applicable as per Section 4.3.9.

### **6.7 Efficacy Analyses**

The efficacy endpoints will include collected and derived continuous and categorical variables. Continuous variables will be summarized by the number of patients, mean, SD, median, minimum and maximum values. Categorical variables will be summarized by absolute counts (n) and percentages (%). Percentages will be based on the number of patients with data.

The ITT Analysis Set will be the primary analysis set of interest in all efficacy analyses, and the primary and secondary efficacy analysis will be repeated on the PP Analyses set. Individual patient listings will be presented for all efficacy data. Data will be summarized by attack, e.g. First attack, second attack, etc.

#### **6.7.1 VAS**

Descriptive statistics for the Overall VAS score and change from Baseline will be presented for each time point for the primary attack location first, followed by each anatomical location separately.

#### **6.7.2 TEQ**

Descriptive statistics for the TEQ responses will be presented for each time point for the primary attack location first, followed by each anatomical location separately.

#### **6.7.3 Investigator Symptom Score**

Descriptive statistics for the IS score will be presented for each time point for the primary attack location first, followed by each anatomical location separately.

#### **6.7.4 Time to Event Analysis**

Kaplan-Meier (KM) analyses will be performed for each of the time to event endpoints (time to beginning of relief and time to minimal symptoms defined using Overall VAS, IS and TEQ, and time to complete resolution). For patients who have been treated for more than one attack, KM analyses for time to beginning of relief and time to minimal symptoms using the Overall VAS score will be repeated for first and last attacks.

Patients who did not have the event of interest will be censored at their last available assessment of that endpoint. For VAS endpoints, in most cases the last available assessment will be at 24 hours post infusion, for IS endpoints it will be 4 hours post infusion.

Additionally, for each endpoint the number and percentage of patients with the event will be presented, along with estimates of the median and quartile time to events with 95% confidence intervals.

#### **6.7.5 Therapeutic Failure**

The number and percentage of patients who experienced therapeutic failure for each attack will be presented alongside a categorical summary of the reasons for failure. A bar chart will also be presented for both first and last attack only.

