12.3.4 Efficacy data

The following analyses will be performed on the basis of the ITT Set and the PP Set, separately for each attack number.

- Kaplan-Meier analysis for time to beginning of relief on the basis of the overall VAS
- Kaplan-Meier analysis for time to minimal symptoms on the basis of the overall VAS
- Kaplan-Meier analysis for time to beginning of relief on the basis of TEQ questions 1 and 2
- Kaplan-Meier analysis for time to minimal symptoms on the basis of TEQ question 3
- Kaplan-Meier analysis for time to complete resolution
- Kaplan-Meier analysis for time to beginning of relief on the basis of the IS
- Kaplan-Meier analysis for time to minimal symptoms on the basis of the IS.
- frequency distribution for therapeutic failure
- descriptive data for each anatomical location:
 - descriptive statistics of the overall VAS at each assessment time, and of the difference between baseline and each assessment after baseline
 - frequency distribution of the IS at each assessment time

The Kaplan-Meier analyses for TTBR and TTMS based on the VAS as well as the frequency distribution of the therapeutic failures will be repeated for the first and last attack for the patients having been treated for more than one attack.

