**Quantitate**  
The Clinical Data Experts

Table Number	Title	Analysis Set	Repeat
Listing 16.2.1	Listing of Patient Disposition	All Patients	Unique
Listing 16.2.2	Listing of Protocol Violations	All Patients	Unique
Listing 16.2.3	Patients Excluded from the Efficacy Analysis	All Patients	Unique
Listing 16.2.4.1	Listing of Demographics and Baseline Patient Characteristics	All Patients	Unique
Listing 16.2.4.2	Listing of Medical History	All Patients	Unique
Listing 16.2.4.3	Listing of Relevant HAE history	All Patients	Unique
Listing 16.2.4.4	Listing of Relevant HAE attack history	All Patients	Unique
Listing 16.2.4.5	Listing of Concomitant Medications	All Patients	Unique
Listing 16.2.5.1	Listing of Study Medication Administration	All Patients	Unique
Listing 16.2.6.1.1	Listing of VAS and change from Baseline in VAS	All Patients	Unique
Listing 16.2.6.1.2	Listing of TEQ	All Patients	Unique
Listing 16.2.6.1.3	Listing of Investigator Symptom Score (IS)	All Patients	Unique
Listing 16.2.6.1.4	Listing of time to event endpoints and therapeutic failure	All Patients	Unique
Listing 16.2.6.2.1	Listing of PK/PD concentrations	All Patients	Unique
Listing 16.2.7.1	Listing of Adverse Events	All Patients	Unique
Listing 16.2.7.2	Listing of Serious Adverse Events	All Patients	Unique
Listing 16.2.7.3	Listing of Adverse Events Leading to Discontinuation from Study	All Patients	Unique
Listing 16.2.8.1	Listing of Clinical Laboratory Parameters	All Patients	Unique
Listing 16.2.8.2	Listing of ECG Parameters	All Patients	Unique
Listing 16.2.8.3	Listing of Vital Signs	All Patients	Unique
Listing 16.2.8.4	Listing of Physical Examination	All Patients	Unique
Listing 16.2.8.5	Listing of HAE Attacks	All Patients	Unique
Listing 16.2.8.6.1	Initial ELISA Immunology Results	All Patients	Unique
Listing 16.2.8.6.2	Neutralizing and Displacement Assay Immunology Results	All Patients	Unique
Listing 16.2.8.6.3	Initial ELISA Immunology Results – Patients with a Confirmed Positive Result	All Patients	Unique
Listing 16.2.8.6.4	Neutralizing and Displacement Assay Immunology Results – Patients with a Confirmed Positive Result	All Patients	Unique
Listing 16.2.8.7	Listing of Diagnostic Parameters	All Patients	Unique
Figure 14.2.1.1.1	Kaplan Meier Plot of Time to Beginning of Relief for First Attack (VAS)	ITT	Unique
Figure 14.2.1.1.2	Kaplan Meier Plot of Time to Beginning of Relief for Last Attack (VAS)	ITT	Repeat of Figure 14.2.1.1.1

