**Quanticate**  
The Clinical Data Experts

Table Number	Title	Analysis Set	Repeat
	(TEQ)		Figure 14.2.1.1.1
Figure 14.2.1.7	Kaplan Meier Plot of Time to Complete Resolution	ITT	Repeat of Figure 14.2.1.1.1
Figure 14.2.1.8.1	Bar Chart of Therapeutic Failure for First Attack	ITT	Unique
Figure 14.2.1.8.2	Bar Chart of Therapeutic Failure for Last Attack	ITT	Repeat of Figure 14.2.1.9.1
Figure 14.2.2.1.1	Boxplot of Functional C1INH (% of Normal) paneled by Time (Linear Scale)	PK/PD Concentration Set	Unique
Figure 14.2.2.1.2	Boxplot of Functional C1INH (% of Normal) paneled by Time (Logarithmic Scale)	PK/PD Concentration Set	Repeat of Figure 14.2.2.1.1
Figure 14.2.2.1.3	Boxplot of Functional C1INH (% of Normal) grouped by Weight and paneled by Time (Linear Scale)	PK/PD Concentration Set	Unique
Figure 14.2.2.1.4	Boxplot of Functional C1INH (% of Normal) grouped by Weight and paneled by Time (Logarithmic Scale)	PK/PD Concentration Set	Repeat of Figure 14.2.2.1.3
Figure 14.2.2.2.1	Boxplot of C4 Concentrations paneled by Time (Linear Scale)	PK/PD Concentration Set	Unique
Figure 14.2.2.2.2	Boxplot of C4 Concentrations paneled by Time (Logarithmic Scale)	PK/PD Concentration Set	Repeat of Figure 14.2.2.2.1
Figure 14.2.2.2.3	Boxplot of C4 Concentrations grouped by Weight and paneled by Time (Linear Scale)	PK/PD Concentration Set	Unique
Figure 14.2.2.2.4	Boxplot of C4 Concentrations grouped by Weight and paneled by Time (Logarithmic Scale)	PK/PD Concentration Set	Repeat of Figure 14.2.2.2.3
Figure 14.2.3	Ratio with respect to Baseline in C4 versus Ratio with respect to Baseline in Functional C1INH	PK/PD Concentration Set	Unique

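### SAP 6.7.5 omits the protocol's restriction of the first/last-attack therapeutic failure display to children treated more than once, so the population of the two bar charts is wrong or undefined

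*SAP*

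**What the plan says.** Protocol 12.3.4 names three analyses to be shown again for first and last attack: Kaplan-Meier for time to beginning of relief (VAS), Kaplan-Meier for time to minimal symptoms (VAS), and the therapeutic failure frequencies. All three "will be repeated for the first and last attack for the patients having been treated for more than one attack".

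SAP 6.7.4 carries this over for the two time-to-event analyses: "For patients who have been treated for more than one attack, KM analyses for time to beginning of relief and time to minimal symptoms" on the Overall VAS are repeated for first and last attacks.

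SAP 6.7.5 first asks for the number and percentage of failures at each attack, with reasons. It then adds: "A bar chart will also be presented for both first and last attack only". It sets no condition on the number of treated attacks.

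Attachment 1 lists Figure 14.2.1.8.1 for the first attack and Figure 14.2.1.8.2, "Bar Chart of Therapeutic Failure for Last Attack", both on the ITT set. SAP 6.7 confirms the default: "The ITT Analysis Set will be the primary analysis set of interest in all efficacy analyses". Under SAP 3.3, one dose and any efficacy data put a child in that set, so children treated once belong to it.

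SAP 7.1, which lists departures from the protocol, mentions only the reduced set of PK parameters.

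**The concern.** Setting first beside last attack shows whether response changes with repeat treatment. That question has meaning only for children who had a repeat treatment. For a child treated once, first and last attack are the same event. If that child is counted in both charts, the result is identical in each and pulls the two percentages together, whatever happened in the children treated repeatedly.

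Repeat treatment matters to this study: Protocol 7.5 ties the end of enrolment partly to having enough repeat-treatment data. The by-attack failure table does not replace the restricted display, because its later columns hold only the children who reached that attack number, while its first column holds everyone.

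**Working it through.** There is no planned figure to reproduce: no sample size was calculated (SAP 2.3) and no hypothesis is tested (SAP 5.2). The check is a comparison of texts followed by algebra.

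**Texts.** The protocol restricts three repeats. The SAP restricts two (6.7.4) and leaves the third unrestricted (6.7.5). No failure table for children treated more than once is listed; Tables 14.2.1.8.1 and 14.2.1.8.2 are the general ITT and PP summaries. Attachment 1 describes Figure 14.2.1.8.2 as a repeat of Figure 14.2.1.9.1, which is not in the list, so the output list does not settle the population either.

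**Notation.** N is the number of ITT children and m the number with at least two treated attacks. Among those m, f1 is the failure proportion at the first attack and fL at the last. Among the N − m children treated once, the failure proportion is s. The documents give none of these except a minimum of 20 treated patients, so N = 20 is used for illustration and the rest are assumptions.

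**Literal reading (single-attack children in both charts).**
- First chart: [m·f1 + (N − m)·s] / N
- Last chart: [m·fL + (N − m)·s] / N
- Difference: (m/N)·(fL − f1)

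The s terms cancel. With an assumed true change of 25 percentage points in either direction:

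| m of 20 | Share m/N | Difference shown (points) |
|---|---|---|
| 4 | 20% | 0.20 × 25 = 5 |
| 8 | 40% | 0.40 × 25 = 10 |
| 10 | 50% | 0.50 × 25 = 12.5 |
| 12 | 60% | 0.60 × 25 = 15 |
| 16 | 80% | 0.80 × 25 = 20 |

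Under the protocol's restriction the factor is 1 and all 25 points are shown, on m children.

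**Counts and ratio.** Take m = 8 with 4 failures at the first attack and 2 at the last, and 3 failures among the 12 children treated once (s = 25%). Restricted: 4/8 = 50% and 2/8 = 25%, a difference of 2 children and a ratio of 0.50. Literal ITT: 7/20 = 35% and 5/20 = 25%, still 2 children, but 10 points and a ratio of 0.71. With s = 0 the ratio stays at 0.50 (4/20 against 2/20). So the percentage-point difference always shrinks, the ratio moves toward 1 unless no single-attack child fails, and the count difference and the sign do not change.

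**Alternative reading (single-attack children in the first chart only).** The difference shown is fL − f1 + [(N − m)/N]·(f1 − s). With m = 8, f1 = 50% and fL = 25%, the true change is −25 points. At s = 25% the charts show −25 + 0.6 × 25 = −10; at s = 75% they show −25 − 0.6 × 25 = −40. The two charts now cover different children and the bias can go either way.

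**The share m/N.** The nearest figure is in Protocol 9.3: 8 of 16 adolescents in the open-label extensions had at least three treated attacks, so at least 50% had more than one. That is a floor for a different age group in other studies, not an estimate for this one.

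**The case against.** The strongest reply is that this concerns one pair of exploratory charts. No test or decision rule depends on them, failure is tabulated for every attack, and Listing 16.2.6.1.4 gives failure for each patient, so anyone can rebuild the restricted comparison. All of that stands, and it limits the weight of the point. It does not explain why a population fixed in the protocol is missing from the SAP.

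A second reply is that the SAP never says single-attack children enter both charts. This also stands. The ITT label alone does not prove it, because the first/last VAS Kaplan-Meier figures carry the same label although 6.7.4 restricts that analysis. The evidence is the missing condition in 6.7.5. Double inclusion is the literal reading of that section, and the shrinkage formula is conditional on it.

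A reader might infer three stronger claims that the documents do not support:

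- *That this is the plan's only check on repeat treatment.* The by-attack summaries and the restricted VAS Kaplan-Meier repeats also address it, and the latter cover the SAP's primary efficacy measure.
- *That the Kaplan-Meier figures have the same fault.* SAP 6.7.4 agrees with the protocol, and all four first/last VAS figures carry the same ITT label, so there is no basis for reading one of a pair as restricted and the other not.
- *That the omission favours the product.* The factor m/N shrinks improvement and deterioration equally.

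**Conclusion.** The omission is clear and undeclared: the protocol's population for the first/last failure display is missing from SAP 6.7.5 and from both figure entries. Neither way of handling single-attack children without the restriction gives the protocol's analysis.

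On the literal reading the percentage-point difference is multiplied by the share of children treated more than once. For shares of 50% to 80%, 50% to 80% of the true difference remains; a share of 20% would leave a fifth. These are illustrations over a range, since the actual share and any true change are unknown. The consequence for interpretation is modest, but the correction is nearly free and changes what the charts show, so it should be made.

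**What to change.** In SAP 6.7.5 and in the entries for Figures 14.2.1.8.1 and 14.2.1.8.2, limit both first and last attack to patients with at least two treated attacks, as Protocol 12.3.4 specifies, and print the common n on both charts. Leave the all-patient by-attack failure table as it is. If the wider population was intended, declare and justify it in 7.1 and say how single-attack children are counted.

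The SOP deviation form attached to the SAP reports that the analysis has been finalised. If the charts already exist, rerun them on the restricted set and explain the change in the clinical study report, the route SAP 7.5 gives for changes after database lock.

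Two additions are optional: naming the same subset in the titles of the first/last VAS Kaplan-Meier figures, and a paired 2x2 count of failure at first against failure at last attack.

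The cost is one sentence and one filter. The downside is that the comparison rests on fewer patients.

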#### **6.7.6 Receipt of a Second Dose**

The number of patients who received a second dose will be summarized using counts and percentages. The Baseline Overall VAS score at the primary attack location, split by attacks treated with a second dose and those that were treated with a single dose, will be summarized using summary statistics.

This will be presented by attack number. In addition, a total column will be presented summarizing all attacks. If a patient has more than one attack they will be included multiple times in this column.

Finally the summary will present the number of patients who had received two doses of rhC1INH for any of their attacks.

## 6.8 Safety Analyses

Unless otherwise stated, safety data will be presented for the Safety Analysis set. Individual patient listings will be presented for all safety data. Where applicable, data will be summarized by attack, e.g. First attack, second attack, etc.

### 6.8.1 Exposure to Study Medication

Exposure to Study Medication will include derived continuous and categorical variables. Continuous variables will be summarized by the number of patients, mean, SD, median, minimum and maximum values. Categorical variables will be summarized by absolute counts (n) and percentages (%). Percentages will be based on the number of patients with data.

Exposure to rhC1INH will be summarized by attack, for both initial and second doses. The following variables will be summarized:

- Total volume of medication administered (mL)
- Total Dose in U/kg (patients who weighed less than 84 kg)
- Total Dose in U/kg (patients who weighed more than or equal to 84 kg)
- Duration of Infusion in minutes (only summarized for Attack 1)

In addition, within the same summary, “Time interval between initial and repeat dose (minutes)” will be summarized under the subtitle “Overall”.

Total exposure will also be summarized across the whole study (i.e. not by attack). In particular the total number of HAE attacks treated with rhC1INH, the total number of rhC1INH doses received and the total dose of rhC1INH will be summarized over all attacks.

The total number HAE attacks treated with rhC1INH and total number of doses of rhC1INH received will be summarized as categorical variables and as continuous variables.

### 6.8.2 Adverse Events

AEs will be recorded throughout the study. These will be coded using the MedDRA dictionary, version 18.0 or later. Tables will only summarize TEAEs; all AEs will be listed.

TEAEs will be summarized using absolute counts (n) and percentages (%). Summaries will be presented by SOC and PT. Results will be sorted by decreasing frequency of the SOC and PT within the SOC.

AE tables will be presented by attack for the Safety Analysis Set. A separate column will be included summarizing AEs reported regardless of attack number. For the overall column, percentages will be presented out of the total number of patients in the Safety Analysis Set and counting will be by patient, so if a patient has the same AE in more than one attack this will only be counted once in the overall column.

The following tables will be produced:

- Overall summary of Adverse Events
- Incidence of Treatment-Emergent Adverse Events
- Incidence of Related Treatment-Emergent Adverse Events
- Incidence of Treatment-Emergent Adverse Events Commencing Within 24 Hours of the Completion of the Infusion of Study Drug Administration
- Incidence of Treatment-Emergent Adverse Events Commencing Within 28 Days of the Completion of the Infusion of Study Drug Administration
- Incidence of Treatment-Emergent Adverse Events by Strongest Relationship (Investigator's Judgment)
- Incidence of Treatment-Emergent Adverse Events by Maximum Severity (Investigator's Judgment)
- Incidence of Treatment-Emergent Serious Adverse Events
- Incidence of Treatment-Emergent Adverse Events Leading to Study Discontinuation
- Incidence of Treatment-Emergent Adverse Events of Special Interest

The Summary of Adverse Events table will be presented by attack and will show the following:

- Number (%) of Deaths
- Number (%) of Treatment-Emergent Deaths
- Number (%) of Subjects With At Least One SAE
- Number (%) of Subjects With At Least One TESAE
- Number (%) of Subjects Who Prematurely Discontinued the Study Due to a TEAE
- Number (%) of Subjects With At Least One TEAE
- Number (%) of Subjects With At Least One Related TEAE
- Number (%) of Subjects Without Any TEAEs

All AEs will be listed. Listings will include CRF collected data, coded terms (primary SOC and PT) and a flag for treatment emergence. The time from last administration of study drug to onset of an AE (hours) will be listed for TEAEs. Separate listings will be produced for any SAEs and any AEs leading to study discontinuation.

### **6.8.3 Clinical Laboratory Parameters**

Clinical Laboratory Parameters include collected and derived quantitative and qualitative parameters. Parameters will be grouped by category (see Table 5 in Section 4.2.3) Quantitative parameters will be summarized by the number of patients, mean, SD, median, minimum and maximum values. Qualitative parameters will be summarized by absolute counts (n) and percentages (%). Percentages will be based on the number of patients with data.

For each attack, data will be summarized by study visit, and the change from Baseline to Day 28 (if visit occurred before the next treatment) will be presented. Frequency distributions of the status (below, within and above the normal range will be presented by study visit, for each attack. A shift table of status at Baseline and Day 28 (if visit occurred before the next treatment) will be presented for each attack.

